8.2. Screening and Enrollment in the Run-in Period (Visit 1)

Subjects who have a confirmed history of micro- or macroalbuminuria (at least two out of three consecutive urinary AER or ACR in micro- or macroalbuminuria range as defined in Section 5.1) will not need to bring a sample of urine to Visit 1. Subjects who have incomplete or no previous evidence of micro- or macroalbuminuria or have unknown albuminuria status, will be mailed two containers before Visit 1 along with instructions for collecting two samples of urine from their first morning void and bringing it to the visit to confirm the presence of micro- or macro-albuminuria. During **Visit 1**, subjects will undergo the following procedures:

- Obtain written informed consent.
- Collect prior and concomitant medications, and demographic information.
- Measure weight and height.
- Measure vital signs.
- Perform pregnancy test in women of childbearing potential.
- Review the fetal risks of RAS blockade.
- Collect samples for clinical laboratory assessment.
- Provide a container and instructions for an overnight urine collection to be made immediately before Visit 3 if subject qualifies for the study.
- Upon receipt of laboratory measurements, confirm that inclusion/exclusion criteria are met.

The Screening Visit can be repeated after 4 weeks if the circumstances that led to the exclusion of a participant are deemed to have possibly changed.

Patients on losartan with uric acid levels between 4.2-4.4mg/dl at initial screening may, with the agreement of the patient and their PCP, be switched to another angiotensin receptor blocker (ARB) and have their uric acid level rechecked in one month.

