8.3. Run-in Period (Visits 2, 3, and 4)

Starting at **Visit 2**, eligible subjects who agree to participate in the study will enter a run-in period of 9 weeks (see note at the end of this section for exceptions to this duration). During this visit, subjects will undergo the following procedures:

- Obtain written informed consent to enter run-in period (if the consent at V1 was only for screening).
- Review the fetal risks of RAS blockade.
- Collect medical history.
- Perform ECG.
- Collect concomitant medications.
- Measure weight and height.
- Measure vital signs.
- Physical Examination
- Obtain a urine pregnancy test

RAS antagonist treatment will be standardized, and BP, if elevated (>140/90 mm Hg), normalized. Letters will be written to the participants' physicians informing them about the study and notifying them of the study's protocol RAS blocker requirements and blood pressure goals. The letter will propose active participation of the participants' physicians in blood pressure management with the

availability of advice from the PERL site physicians and, if needed, the PERL Drug monitoring Committee for out of range blood pressure values during the course of the study. The run-in period will start at **Visit 2**. If a participant is already on a RAS Blocker, its dose will be increased, if necessary, to make it at least equivalent to ramipril 10 mg (if on ACE inhibitor [ACEI]) or irbesartan 300 mg (if on an angiotensin receptor blocker [ARB]), if acceptable to the patient's primary physician, if tolerated and if not contraindicated (see below). Participants who were not taking a RAS Blocker will be prescribed and instructed to start taking 10 mg of ramipril daily or 300 mg of irbesartan daily (if ramipril is contraindicated or has side effects) or another ACE inhibitor or ARB at equivalent doses if there are impediments to the use of ramipril or irbesartan. Participants who have contraindications to RAS blockers (e.g., SBP<100 mmHg, K⁺>5.5 mEq) or do not have evidence or history of micro- or macroalbuminuria (as defined in 5.1.4), are normotensive, and are not being treated with RASB or other anti-hypertensive agents will not be treated with these drugs, as this represents the standard of care.

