Participants who are placed for the first time on RAS blockers as part of this study will start with half a dose; if there are no side effects, this will be increased to a full dose at Visit 3 and their serum K⁺ and creatinine measured at a local laboratory after 2 weeks. RAS blockers will be immediately discontinued in the case of allergic reactions or angioedema or the suspicion of pregnancy. If pregnancy is confirmed, the patient will remain off RAS blockade until the pregnancy and breast-feeding are completed. Their dose will be decreased to half if symptomatic hypotension (SBP<100%) or intractable cough develops, followed by their discontinuation. For persistent cough with ramipril or other ACEI, irbesartan or another ARB will be prescribed in substitution of the ACEI.

In the case of hyperkalemia (K⁺ >6.0 mEq) or serum creatinine elevation (>30% increase over baseline values), the participant will be asked to immediately obtain a confirmatory lab value at their local lab or clinical site and then discontinue the RAS blocker while awaiting this confirmatory result. If confirmed, the participant will resume RAS blockade at half dose 72 hours later and will have repeat labs one week later. If the problem persists, RAS blockade will be discontinued for the remainder of the trial and BP managed by alternate drugs (see below). If not confirmed, the participant will resume RAS blockade at their usual dose and have a repeat lab check one week later. These same steps will be taken if hyperkalemia develops during the trial.

Participants will continue to take any other antihypertensive drug that they may have been taking before study entry. Participants will be provided with a blood pressure monitoring device (if they do not already have access to one), will be trained on its use, and will be instructed to periodically monitor their blood pressure at home and to record the results into a BP diary, and to communicate them to study personnel if values are abnormal.

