13.4.3. Risks associated with RAS blocker treatment

Treatment with RAS blockers (either ACE inhibitors such as ramipril or angiotensin receptor blockers such as irbesartan) is currently the standard of care for diabetic individuals who have micro- or macroalbuminuria. The risk associated with the use of these drugs during the trial will not be greater than the risks participants would face outside the trial by being treated with these agents. These risks include allergic reactions, hyperkalemia, hypotension, increased serum creatinine, persistent cough (with ramipril), liver damage, bone marrow depression, and fetal and neonatal morbidity and death when RAS

blockers are taken during pregnancy. The occurrence of these adverse events will be monitored during the trial.

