- j. Most of the participants will already be on RAS Blockers. For those who were not previously taking these medications, risks will be minimized by not prescribing RAS Blockers to participants who have contraindications to these drugs and by prescribing an ARB whenever ACE inhibitors are contraindicated. If adverse events develop that are deemed to be related to the use of RAS blockers, the dose of these drugs will be decreased, followed by their discontinuation if the problem persists (see 8.2. Run-in period), thus adhering to current standards of care. If receiving discontinuation of RAS blockade becomes necessary, BP will be managed by alternate drugs as described above.
- k. Blood pressure will be measured quarterly with the goal of maintaining BP ≤ 140 mmHg systolic and ≤ 90 mmHg diastolic. If elevated, a recheck will be performed within 2 weeks and if still elevated additional antihypertensive non-RAS blockers will be added in collaboration with the participants' physicians. Failure to achieve satisfactory BP control within 2 months would lead to a case review by the Drug Monitoring Committee.
- l. Participants with a decrease in both iGFR (meeting the R^2 criterion described in 7.1.2) and eGFR from one measurement to the following one corresponding to a GFR decline $> 20\%$ per year will be referred to a nephrologist to investigate the causes of such rapid loss of kidney function. If a decrease of such magnitude is observed for the iGFR but is less than a 20%

decline per year for the eGFR, the iGFR measurement will be repeated. If the >20% per year iGFR decrease is confirmed, the participant will be referred to a nephrologist for further evaluation. In this case, the first iGFR value will be used for the analysis of the primary outcome. If the >20% per year iGFR decrease is not confirmed, the participant will not be referred to a nephrologist. The first iGFR test will be reviewed to verify whether medical conditions that should have prompted a test postponement, such as dehydration or recent use of NSAID (see 7.1.1.3), were present. In that case, the repeated iGFR value will be used for the primary outcome analysis. Otherwise, the first iGFR value will be used.

- m. Data monitoring will be performed on a regular basis. Data entry computers will be programmed to flag any parameters outside clinically acceptable ranges.

c. Protection of confidentiality

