- h. To minimize the risk of liver injury, subjects with clinically significant hepatic disease and/or elevated liver enzymes above 2.5 x the upper limit of normal at the screening visit will be excluded from the study. In those subjects that are enrolled in the study, liver enzyme levels will be monitored at each follow-up visit. If levels are abnormal, the measurement will be repeated and if values are confirmed to be elevated the study drug will be discontinued. The Drug Monitoring Committee will review each case and decide whether a referral to a hepatologist is warranted and whether study treatment can be reinstated after enzyme values have returned to normal on the recommendation of a hepatologist.
- i. To minimize the impact of blood draws, participants with low hemoglobin levels (<11 g/dL in males, <10 g/dl in females) will be excluded. Subjects will be advised not to donate blood while participating in the study and for two months after their participation has ended. If they have just donated blood, their screening for the study will be delayed by 3 months. Hemoglobin levels will be monitored quarterly.
- j. Most of the participants will already be on an ACE inhibitor. Thus, switching them to another drug of the same class (ramipril) should not pose significant risks. In the remaining participants (taking an Angiotensin Receptor Blocker [ARB] or not taking any RAS Blockers), risks will be minimized by not prescribing RAS Blockers to participants who have contraindications to these drugs and by prescribing an ARB (irbesartan) whenever ACE inhibitors are contraindicated. If adverse events develop that are deemed to be related to the use of RAS blockers, the dose of these drugs will be decreased, followed by their discontinuation if the problem persists (see 8.2. Run-in period), thus adhering to current standards of care. If receiving discontinuation of RAS blockade becomes necessary, BP will be managed by alternate drugs as described above.
- k. Blood pressure will be measured quarterly with the goal of maintaining BP <130 mmHg systolic and <85 mmHg diastolic. If elevated a recheck will be performed within 2 weeks and if still elevated additional antihypertensive non-RAS blockers will be added from a limited menu of agents as prescribed in the MOO. Failure to achieve satisfactory BP control within 2 months would lead to a Drug Monitoring Committee conference call. The patient's physicians would be asked to

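### Protocol Section 13.5.b.7.j gives one reduce-then-stop order for RAS-blocker adverse events, which reverses Section 8.3 for allergy or angioedema, omits its interruption for potassium and creatinine events, and cites the wrong section

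*Protocol*

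**What the plan says.** Section 13.5.b.7.j of the current protocol, in the part on minimizing participant risk, sets its rule for adverse events judged "related to the use of RAS blockers, the dose of these drugs will be decreased, followed by their discontinuation if the problem persists", and adds a pointer to the run-in period, which it numbers 8.2. It names no event to which a different order applies.

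Section 8.3 sets rules by event. For the most acute it says "RAS blockers will be immediately discontinued in the case of allergic reactions or angioedema or the suspicion of pregnancy". For potassium above 6.0 mEq or a creatinine rise of more than 30% over baseline, the participant gets a confirmatory sample and must "then discontinue the RAS blocker while awaiting this confirmatory result". If the finding is confirmed, the drug restarts at half dose 72 hours later, and it is stopped for the rest of the trial if the problem continues. If the finding is not confirmed, the usual dose resumes. For symptomatic hypotension and intractable cough, the dose is halved and the drug is then stopped.

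Section 13.4.3 lists what the protocol regards as RAS-blocker risks: "These risks include allergic reactions, hyperkalemia, hypotension, increased serum creatinine, persistent cough (with ramipril), liver damage, bone marrow depression", followed by fetal and neonatal harm.

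**The concern.** The study itself introduces or raises RAS blockade during run-in, so it is responsible for giving sites one clear instruction when that treatment causes harm. The participant-protection section and the operational section do not give the same first action for every event. A site that followed 13.5.b.7.j to the letter for angioedema would lower the dose and wait to see whether the problem continued, whereas 8.3 stops the drug immediately. The pointer that might settle the matter carries the wrong section number.

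The time scope makes this worse. Section 8.3 is headed as the run-in section, yet Section 8.6 keeps RAS therapy going until Visit 17. Section 8.3 expressly carries its hyperkalaemia steps and its blood-pressure management into the rest of the trial. It does not do so for allergy or angioedema, or for a creatinine rise. Section 13.5 has no time limit. For an allergic reaction in year 2, a site could reasonably take 13.5 as the governing text.

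**Working it through.** No arithmetic is involved beyond a count. The check sets the two sections of the current protocol side by side, event by event.

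| Event | 13.5.b.7.j | 8.3 | Comparison |
|---|---|---|---|
| Allergic reaction or angioedema | Reduce, then stop if it persists | Stop at once | First action reversed |
| Potassium > 6.0 mEq | Reduce, then stop if it persists | Confirmatory sample and hold; if confirmed, half dose 72 hours later; stop if it persists | Same path after a hold that 13.5 omits |
| Creatinine rise > 30% | Reduce, then stop if it persists | As for potassium | Same path after a hold that 13.5 omits |
| Symptomatic hypotension | Reduce, then stop if it persists | Halve, then stop | Agree |
| Intractable cough | Reduce, then stop if it persists | Halve, then stop | Agree |

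Count: 1 reversed + 2 lacking the interruption + 2 in agreement = 5 event types. On hypotension, a later paragraph of 8.3 reduces other antihypertensives first, but the RAS blocker itself is still halved before it is stopped.

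**Does the general sentence reach these events?** Section 13.4.3 names allergic reactions, hyperkalaemia and raised creatinine as RAS-blocker risks, so they fall within it. Angioedema is not named there, but 8.3 pairs it with allergic reactions.

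**Does another item of 13.5 supply the missing exception?** Item b of the same list deals with allergic reactions, but what it stops is the study medication. It says nothing about the RAS blocker.

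**Is the pointer usable?** It names the run-in period but numbers it 8.2. Section 8.2 is titled "8.2. Screening and Enrollment in the Run-in Period (Visit 1") and has no rule for RAS-blocker adverse events. The rules are in the next section, "8.3. Run-in Period (Visits 2, 3, and 4").

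**Is this superseded text?** No. The same sentence and pointer appear in the December 17, 2013 version, and both remain in the current one although the opening of item j was rewritten in between.

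**The case against.** The strongest reply is that 13.5.b.7.j is a summary for human-subjects purposes that defers to the run-in rules. It calls the run-in section by name, only the number is off by one, and a clinician who sees angioedema is likely to follow the explicit rule in 8.3. This has force on likelihood: nothing in the documents shows that a site would act on 13.5 instead. It does not remove the contradiction, because the sentence states no exception and changes the first action for allergy.

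The reply is stronger on extent. A reader might infer that 13.5 states the opposite order for four of six event types, counting suspected pregnancy. The documents do not support that:

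- **Pregnancy.** Section 13.5.b.7.a already tells participants to stop RAS blockers at once after a period missed by more than two weeks. Pregnancy is also not naturally a drug-related adverse event.
- **Potassium and creatinine.** After the hold, 8.3 follows the 13.5 path. What differs is the interruption: the wait for the result and, if confirmed, the 72 hours.
- **Liver damage and bone marrow depression.** Section 8.3 has no RAS-blocker rule for these, so there is nothing to contradict.

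**Conclusion.** The current protocol contradicts itself on handling RAS-blocker adverse events. The clear reversal is allergy or angioedema, one of the five event types. For hyperkalaemia and creatinine rise, 13.5.b.7.j leaves out an interruption that 8.3 requires. For hypotension and cough the two sections agree. The cross-reference is wrong.

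The conclusion assumes that the sentence in 13.5.b.7.j is read as written. Only participants who take a RAS blocker and have one of the three affected events could be touched, and the documents give no counts.

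A reader might also infer that differing RAS exposure would disturb the GFR results. The documents do not support a claim of that kind: they give no size for it, the potassium and creatinine difference is a short hold within a 3-year treatment period, and sites are blinded to allocation (Section 6.2). The case for correction is participant safety and consistent instructions, not bias or loss of power.

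**What to change.** The sponsor's clinical team should reconcile 13.5.b.7.j with 8.3 so that one sequence is stated for each event, and say for each whether it applies after run-in. The pointer should be changed from 8.2 to 8.3. The new wording should not simply assume that either section prevails; that is a clinical decision, and no view is taken here. If the general sentence is reworded, the team should check what then covers liver damage and bone marrow depression, since at present it is the only RAS-blocker instruction that reaches them.

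The cost is about one sentence and one corrected section number, in an amendment or a memo to sites. It needs no extra visits or tests and no change to the SAP.

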13.7. Institutional Review Board

The protocol and informed consent forms and subsequent modifications will be reviewed and approved by the Human Subject Committees at all the centers involved in the study for compliance with applicable standards/regulations.

14. DATA AND SAFETY MONITORING PLAN

The Data and Safety Monitoring Plan for this study includes the following elements:

1. A *Data Safety Monitoring Board (DSMB)*, including outside experts in the design and conduct of clinical trials and in diabetic nephropathy, will be established by NIH. The purpose of the DSMB is to assure independent review as to whether study patients are exposed to unreasonable risk because of study participation, and to monitor study progress and integrity. The DSMB will receive detailed data from the Data Coordinating Center as frequently as deemed appropriate by the board, including summary tabulations and narratives of adverse events, and will meet periodically with the Study Investigators and the Data Coordinating Center personnel. They will have full access to all data, and their recommendations and input will be given high priority and will be incorporated into the study protocol. To this end, the DSMB will meet separately, *"in camera"* (Closed Sessions), with the Co-Director of the Data Coordinating Center, [name], to review all adverse event data in relation to the randomized treatment groups in order to detect any increased frequency of significant adverse events which could be study drug related, and decide whether continuation of the trial is warranted.
2. *IRB monitoring* will be in place from:
 - ◆ Joslin Diabetes Center
 - ◆ University of Minnesota
 - ◆ University of Colorado
 - ◆ University of Michigan
 - ◆ Northwestern University
 - ◆ University of Toronto
 - ◆ Albert Einstein College of Medicine
 - ◆ Steno Diabetes Center
3. *SAE reporting.*
All adverse events are reported to the DCC by completion of the Adverse Events Form. All SAEs as defined previously will require expedited event notification within 72 hours of occurrence or identification to the DCC. The DCC will promptly notify the study PIs, who may convene a Drug Monitoring Committee (DMC) conference to acquire further information about the event and take appropriate actions concerning the study medication (see Section 15.1).

An independent physician not involved in the study will serve as the Medical Safety Officer, reviewing all SAEs promptly after being reported in the database by the clinical sites. Based on the clinical site report and any additional input from the DMC, the Medical Safety Officer will prepare a preliminary SAE narrative report (in cases where the SAE is not resolved) for each SAE which will be distributed to the PIs, NIDDK Program Director, DSMB Chair, clinical site director, and appropriate DCC staff. Once the SAE is resolved, a final SAE narrative report is generated by the Medical Safety Officer. This report will be sent to the clinical site PI to review for accuracy and completeness. Following review by the clinical site PI, the Medical Safety Officer will send the final SAE narrative report to the PIs, NIDDK Program Director, DSMB Chair, clinical site director, and appropriate DCC staff. All SAE narrative reports, both preliminary and final, will be reviewed by the DSMB during their regularly scheduled meetings or on an expedited basis as determined by the NIDDK Program Director, who will solicit the input of the Chair of the DSMB as needed. The FDA definitions and requirements for expedited reporting will be used to determine if any individual SAE warrants notification to the FDA and to the IRBs of all participating PERL clinical sites.

The clinical site at which the SAE occurred is responsible for expedited reporting of the SAE to their respective IRB. Each site is responsible to report all AE's to their IRB according to its AE reporting policy and procedures.

On behalf of the NIDDK, the Data Coordinating Center will submit an expedited safety report to the FDA for all serious unexpected suspected adverse reactions (SUSARs). That is, when the SAE is unexpected and may be related to the study drug based on evidence of causality. This report will include information

on frequency of similar events along with a narrative of similar events to provide context for the individual report. Copies of the expedited safety report will be provided to the PIs, NIDDK, DSMB, and site investigators.

4. When collecting data on participants, adequate safety levels will be set for flagging test results. When these levels are reached, the Data Coordinating Center will notify the appropriate clinic that an abnormal result has been received. Detailed follow-up procedures will be set in the Manual of Operations that will be followed by the clinic when any abnormal results are received.
5. Monthly conference calls will be scheduled for the Steering Committee (SC) and the Trial Coordinators. Subject participation and compliance will be discussed in detail during these calls. A clinical psychology expert in the behavioral and compliance aspects of clinical trials, [name] from the University of Minnesota, will be included in the Trial Coordinator calls when discussing participant compliance issues.
6. A Drug Monitoring Committee (DMC) consisting of the PERL Center Directors and PIs, a research pharmacist, and the Project Manager will hold conference calls regarding any serious medication related problem that a participant has. Changes in study medication dose, medication discontinuation and medication re-institution will be discussed during these calls.
7. Twice a year, the Study Group will meet face-to-face with the Data Coordinating Center personnel for a 1½ day meeting to discuss the study in detail and any problems that may have occurred. The Trial Coordinators will hold a separate ½ day meeting with the Data Coordinating Center prior to the SC meeting and any issues needing discussion will be presented at that time and carried from and to the main Study Group meeting for discussion and resolution.

